1    **Official Title**

2    **Influenza Vaccination Effectiveness of a Quadrivalent Inactivated Vaccine in**  
3    **Pregnant Women and Young Infants (Aged 6 months and Below) During**  
4    **Influenza Season 2019-2020**

5

6    **Unique Protocol ID: 16708**

7    **6 May 2021**

8

9

10

11

12

13

14

15

16

17

18

19

20 **Statistical analysis**

21 Women were excluded from the statistical analysis for the following reasons that  
22 occurred before the onset of influenza season: decision to withdraw from the study,  
23 loss to follow-up, post-partum influenza vaccination (cocooning), pregnancy  
24 discontinuation, spontaneous abortion, perinatal death. Women were followed for the  
25 entire influenza season, regardless of onset of influenza or ILI. The analysis was  
26 restricted to the influenza season. The primary outcome of the study was influenza  
27 onset in pregnant women. Secondary outcomes were the onset of influenza in their  
28 infants and the onset of ILI, ARI, febrile episode, pneumonia, healthcare seeking,  
29 hospitalization, use antibiotics and use of antivirals in pregnant women and their  
30 infants. Categorical and continuous variables were compared between vaccinated and  
31 unvaccinated groups using the  $\chi^2$  test and T-test, respectively. Logistic regression  
32 analysis was conducted in order to identify factors significantly associated with a  
33 history of influenza vaccination in 2019-2020. Odds ratio (OR) and confidence  
34 intervals (CIs) were estimated. We have used a Bayesian model selection for logistic  
35 regression models with random intercept. The primary outcome of interest was to  
36 estimate the average rate of influenza for each group (vaccinated versus unvaccinated  
37 group). Our data was a 2 by 2 cross-tabulated data arising from two binary variables  
38 with possible values 0 or 1. The first variable was whether a pregnant woman has  
39 been vaccinated (value =1) or not (value =0). The second variable was the age group  
40 of the pregnant woman. The first group consisted of pregnant women aged less than  
41 32 years (value =0) or not (value=1). We compared the vaccinated pregnant women  
42 group with the group of non-vaccinated pregnant women to model the proportion of  
43 effectiveness that is the event that a pregnant woman had influenza. We used the  
44 Bayesian beta-binomial model due to data heterogeneity because of a large number of

45 zeros were observed. Given this heterogeneity assumption, a Bayesian hierarchical  
46 random-effects model was used to analyze the data. The assumption of our model  
47 was that the number of individuals  $y_j$  responding to influenza vaccination is  
48 binomially distributed as:

49  $y_j \sim \text{Binomial}(p_j, n_j)$ ,

50 where the success rate ( $p_j$ ) was the probability of influenza onset in mothers and  $n_j$   
51 was the number of individuals in the  $j$ th group. We note that there are only 2 groups  
52 ( $j=1,2$ ): the vaccinated and the not vaccinated groups. The probability ( $p_j$ ) itself  
53 follows a beta distribution with parameters ( $a_j, b_j$ ). Non-informative distributions  
54 priors distributions were placed on the parameters of the beta distributions. P-values  
55 of 0.05 or less were considered statistically significant. IVE against influenza was  
56 estimated as follows:  $[1 - (\text{incidence rate of influenza in vaccinated women} / \text{incidence rate of influenza in unvaccinated women})] \times 100$  [11]. The statistical analysis was  
57 conducted using R 3.6 (R Foundation for Statistical Computing).  
58

59

60

61 **Results**

62 A total of 949 pregnant women were enrolled in the study (Figure 1). Of them, 94  
63 women were excluded from the analysis because of the following reasons: lost to  
64 follow-up or decision to withdraw from the study (65 women), post-partum influenza  
65 vaccination (cocooning) (25 women), spontaneous abortion (3 women), and perinatal  
66 death (1 woman). Therefore, 855 pregnant women were included in the analysis.  
67 Their mean age was 32.9 years (range: 18-45 years) and their mean gestational age at  
68 enrollment was 23.3 weeks (range: 3-39 weeks).

69 Of the 855 pregnant women, 525 (61.4%) were vaccinated against influenza and 330  
70 (38.6%) refused vaccination. No serious adverse event occurred. Pregnant women  
71 with a history of influenza vaccination the past (2018-2019) season were more likely  
72 to get vaccinated against influenza in 2019-2020 compared to women with no history  
73 of vaccination (91.8% versus 55.1%, p-value<0.001). In the logistic regression  
74 analysis the following variables were significantly associated with a history of  
75 influenza vaccination in 2019-2020: lower gestational age (OR: 0.998; CI: 0.998-  
76 0.999), influenza vaccination the past season (OR: 8.8; CI: 4.7-16.2), and no smoking  
77 during pregnancy (OR: 0.6; CI: 0.4-0.9).

78 ***Estimation of IVE in pregnant women***

79 Of the 855 pregnant women included in the analysis, 636 women were still pregnant  
80 during the 2019-2020 influenza season and comprised the study group for the  
81 estimation of IVE in pregnancy. Of them, 406 women (63.8%) were vaccinated  
82 against influenza and 230 (36.2%) refused vaccination. Table 1 shows their  
83 characteristics by influenza vaccination status.

84 Twelve of the 636 pregnant women tested positive for influenza (8 cases of influenza  
85 A/H3N2, 2 cases of A/H1N1 and 2 cases of influenza B). Table 2 summarizes their  
86 morbidity by influenza vaccination status. The incidence of influenza differed  
87 between vaccinated women (6/406; 1.47%) and unvaccinated women (6/230; 2.6%),  
88 however the difference was not statistically significant. Similarly, higher rates of  
89 febrile episode, ILI, pneumonia, healthcare seeking, hospitalization, use of antibiotics  
90 and antivirals were noted in the unvaccinated group compared to the vaccinated  
91 group, however none of these differences reached statistical significance (Table 2).  
92 The IVE of QIV against influenza was 43.5% for pregnant women during 2019-2020  
93 in Greece. The IVE of QIV against influenza was 43.5% (95% CI: 28.4%-55.6%) for  
94 pregnant women during 2019-2020 in Greece.

95 According to the regression model the age was not a predictor of influenza onset in  
96 the sample of pregnant women. Influenza vaccination of pregnant women reduced  
97 their logit to develop influenza by -4.2 (95% CI -3,7 -4,7), which indicates that  
98 influenza vaccination added a statistically significant protection to pregnant women.

99 ***Estimation of IVE in infants***

100 A total of 474 infants were born before or during the 2019-2020 influenza season and  
101 constituted the group for the estimation of IVE in infants. Their mean birth weight  
102 was 3189 g (range: 630-4650 g) and their mean gestational age was 39.1 weeks  
103 (range: 28-42 weeks). There were 281 (59.3%) infants whose mothers were  
104 vaccinated during pregnancy and 193 (40.7%) infants of unvaccinated mothers. The  
105 unvaccinated mothers had a mean gestational age of 31.2 weeks at enrollment  
106 compared to a mean gestational age of 28.3 weeks of vaccinated mothers (p-value

107 <0.001); no other significant difference was noted between the two groups (data not  
108 shown).

109 Overall, 8 of the 474 infants tested positive for influenza (5 cases of influenza  
110 A/H3N2, 2 cases of influenza A/H1N1 and 1 of influenza B). Table 3 summarizes  
111 their morbidity by maternal influenza vaccination status. Infants of unvaccinated  
112 mothers more often developed influenza, febrile episodes, ILI, ARI, AOM and  
113 pneumonia and had increased rates of healthcare seeking, hospitalization, use of  
114 antibiotics and use of antiviral agents compared to infants whose mothers were  
115 vaccinated, however these differences reached statistical significance only for ARI  
116 and use of antiviral agents (p-values=0.012 and 0.036, respectively). The IVE against  
117 influenza for infants was estimated at 31.4% in 2019-2020. The IVE against influenza  
118 for infants was estimated at 31.4% (95% CI: 4%-51%) in 2019-2020.

119 According to the regression model the age of pregnant women was not a predictor of  
120 influenza onset in the sample of young infants. Additionally the influenza vaccination  
121 of pregnant women reduced the logit of their infants to develop influenza by -4.2  
122 (95% CI -3.6, -4.9), which indicates that influenza vaccination during pregnancy  
123 added a statistically significant protection to young infants.

124

125

126

127

128

129 **Table 1. Characteristics of pregnant women (n=636) by influenza vaccination status**130 **Characteristic** **Vaccinated** **Unvaccinated** **P-value**131 **n=406 (%)** **n=230 (%)**

132 \_\_\_\_\_

133 Mean age, years (range) 33.1 (21-45) 32.3 (18-45) 0.055

134 Mean gestational age, weeks (range) 19.3 (3-39) 21.6 (3-39) 0.003

135 Underlying disease 49 (12.2) 32 (14.0) 0.512

136 Influenza vaccination the past season 94 (23.2) 14 (6.1) <0.001

137 Mean no. of cohabitants (range) 1.7 (0-8) 1.8 (0-8) 0.147

138 Children <5 years 161 (39.8) 79 (34.5) 0.190

139 Mean no. of children <5 years (range) 0.5 (0-3) 0.4 (0-3) 0.325

140 No smoking during pregnancy 350 (93.1) 173 (84.0) 0.001

141 142 Smoking during pregnancy 26 (6.9) 33 (16.0)

143 \_\_\_\_\_

144

145

146

147

148

149

150

151 **Table 2. Morbidity (%) of pregnant women (n=636) by influenza vaccination status**

152	Type of morbidity	Vaccinated	Unvaccinated	P-value
153		n = 406 (%)	n = 230 (%)	
154	Influenza*	6 (1.5)	6 (2.6)	0.314
155	Febrile episode	17 (4.2)	13 (5.7)	0.402
156	ARI	115 (28.3)	50 (21.7)	0.069
157	ILI	11 (2.7)	11 (4.8)	0.169
158	Pneumonia	2 (0.5)	4 (1.7)	0.118
159	Healthcare seeking	5 (1.2)	5 (2.2)	0.359
160	Hospitalization	0 (0.0)	1 (0.4)	0.184
161	Use of antibiotics	11 (2.7)	7 (3.0)	0.807
162	Use of antivirals	3 (0.7)	4 (1.7)	0.245

163

164 \* laboratory-confirmed influenza

165 ARI: acute respiratory infection; ILI: influenza-like illness

166

167

168

169

170 **Table 3. Morbidity (%) of infants (n=474) by maternal influenza vaccination status**

171	Type of morbidity	Vaccinated	Unvaccinated	P-value
172		n = 281 (%)	n = 193 (%)	
173	Influenza*	4 (1.4)	4 (2.1)	0.59
174	Febrile episode	7 (2.5)	8 (4.1)	0.312
175	ARI	17 (6.0)	27 (14.0)	0.012
176	ILI	6 (2.1)	6 (3.1)	0.507
177	AOM	1 (0.3)	2 (1.0)	0.358
178	Pneumonia	0 (0.0)	1 (0.5)	0.227
179	Healthcare seeking	6 (2.1)	10 (5.2)	0.144
180	Hospitalization	0 (0.0)	1 (0.5)	0.277
181	Use of antibiotics	4 (1.4)	5 (2.6)	0.360
182	Use of antivirals	0 (0.0)	3 (1.6)	0.036

183

184 \* laboratory-confirmed influenza

185 ARI: acute respiratory infection; ILI: influenza-like illness; AOM: acute otitis media

186

187

188

189

190

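### The SAP has no rule for sparse tables or continuity correction; the infant antiviral result (p = 0.036, three events) depends on that choice, and three Table 3 p-values do not follow from their counts

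*SAP*

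**What the plan says.** The Statistical analysis section sets a single rule for all simple group comparisons: "Categorical and continuous variables were compared between vaccinated and" "unvaccinated groups using the $\chi^2$ test and T-test, respectively". It names no exact test, gives no expected-count threshold, and does not say whether a continuity correction applies. The significance threshold in the same section is that p-values "of 0.05 or less were considered statistically significant".

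The rule is applied to nine maternal outcomes in "Table 2. Morbidity (%) of pregnant women (n=636) by influenza vaccination status" and to ten infant outcomes in Table 3. The group sizes are 406 and 230 women ("Of them, 406 women (63.8%) were vaccinated") and 281 and 193 infants ("There were 281 (59.3%) infants whose mothers were"). For infants, the text under Estimation of IVE in infants says that only two differences reached significance, ARI "and use of antiviral agents (p-values=0.012 and 0.036, respectively). The IVE against". The antiviral row of Table 3 reads "0 (0.0) 3 (1.6) 0.036".

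**The concern.** Most of the morbidity outcomes are rare. The SAP recognises this for influenza, where it cites the large number of zeros as a reason for a beta-binomial model, but it leaves the table-by-table comparisons on an unqualified large-sample test. When a table holds very few events, the p-value depends noticeably on which form of the test is used. If the plan does not fix the form, two analysts can follow it faithfully and report different answers.

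At stake is one of only two infant differences that the text calls significant. The same recomputation also tests whether the printed p-values are the ones that the stated rule produces.

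**Working it through.** **Inputs.** Event counts and group sizes come from Tables 2 and 3 of the SAP; the threshold is 0.05. The SAP does not state sidedness; all tests here are two-sided.

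**Step 1: reproduce the printed p-values.** Pearson's statistic for a 2×2 table with rows (a, b) and (c, d) is N(ad − bc)² / (r₁ r₂ c₁ c₂), where r and c are the row and column totals. For infant antivirals, (0, 281) and (3, 190):

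- 474 × (0 × 190 − 281 × 3)² / (281 × 193 × 3 × 471) = 474 × 843² / 76,631,229 = 4.396, so p = 0.0360, as printed.

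Uncorrected Pearson reproduces all nine Table 2 values and seven of the ten in Table 3 (AOM is 0.359 against 0.358 printed, which is immaterial). The uncorrected form was therefore used, although the SAP does not say so.

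**Step 2: find the sparse tables.** Smallest expected count = smaller group × total events / N. For maternal influenza: 230 × 12 / 636 = 4.34. For infant antivirals: 193 × 3 / 474 = 1.22. Tables with a value below 5:

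| Outcome | Events (vaccinated, unvaccinated) | Smallest expected | Printed p | Fisher p |
|---|---|---|---|---|
| Women: influenza | 6, 6 | 4.34 | 0.314 | 0.37 |
| Women: pneumonia | 2, 4 | 2.17 | 0.118 | 0.196 |
| Women: healthcare seeking | 5, 5 | 3.62 | 0.359 | 0.508 |
| Women: hospitalization | 0, 1 | 0.36 | 0.184 | 0.362 |
| Women: antivirals | 3, 4 | 2.53 | 0.245 | 0.261 |
| Infants: influenza | 4, 4 | 3.26 | 0.59 | 0.721 |
| Infants: ILI | 6, 6 | 4.89 | 0.507 | 0.560 |
| Infants: AOM | 1, 2 | 1.22 | 0.358 | 0.570 |
| Infants: pneumonia | 0, 1 | 0.41 | 0.227 | 0.407 |
| Infants: hospitalization | 0, 1 | 0.41 | 0.277 | 0.407 |
| Infants: antibiotics | 4, 5 | 3.66 | 0.360 | 0.496 |
| Infants: antivirals | 0, 3 | 1.22 | 0.036 | 0.067 |

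That is 5 of 9 plus 7 of 10, or 12 of 19 tables. Only the last row crosses 0.05. No Table 1 comparison is sparse (smallest expected count about 21).

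**Step 3: infant antivirals under other tests.**

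- Fisher: probability of the observed split = (193 × 192 × 191) / (474 × 473 × 472) = 0.0669. The opposite extreme (3 versus 0) has probability 0.207, so it is not added, and p = 0.067. With three events, 0 versus 3 is the most extreme split favouring vaccination, so Fisher's test could not have reached 0.05 in that direction.
- Yates: 474 × (843 − 474/2)² / 76,631,229 = 474 × 606² / 76,631,229 = 2.272, p = 0.132.
- Mid-p: 0.0669 / 2 = 0.033.
- Barnard's unconditional test (pooled z, maximum over the common rate): 0.037.
- One event among the vaccinated (1 versus 3): Pearson = 474 × 650² / (281 × 193 × 4 × 470) = 1.964, p = 0.16.

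**Step 4: Table 3 values that do not reproduce.**

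| Infant outcome | Counts | Printed | Pearson | Yates | Fisher |
|---|---|---|---|---|---|
| ARI | 17/281, 27/193 | 0.012 | 0.0034 | 0.0057 | 0.0056 |
| Healthcare seeking | 6/281, 10/193 | 0.144 | 0.071 | 0.122 | 0.118 |
| Hospitalization | 0/281, 1/193 | 0.277 | 0.227 | 0.850 | 0.407 |

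None of the three tests gives the printed figure in any row. Infant hospitalization and infant pneumonia have identical counts (0 versus 1) yet are printed as 0.277 and 0.227.

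**The case against.** The strongest reply is that an expected-count threshold is only a rule of thumb and that Fisher's test is itself conservative. This has force. For groups of 281 and 193, the true size of the uncorrected chi-square test at nominal 5% is 2.7% at a common rate of 3/474, 3.9% at 1% and 4.97% at 2%, so the test does not exceed its nominal error rate at these low rates. Mid-p is lower than chi-square in several rows (maternal influenza 0.297 against 0.314), and mid-p and Barnard both keep infant antivirals below 0.05.

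A reader might therefore infer too much from the sparse tables. The documents and the arithmetic do not show that chi-square was the wrong test, that the printed p-values are generally too small, or that the antiviral result is an artefact. Nor are most expected counts below 5: 20 of 76 cells are. The statement that holds is about tables containing at least one such cell.

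It is also fair to say that the consequence is limited. The primary outcome is reported as non-significant by the simple comparison under either test, it has a separate Bayesian analysis, and antiviral use is one secondary outcome. What survives is that the plan does not settle the form of the test and that one reported conclusion turns on it. The Step 4 discrepancies are untouched by this reply: ARI and healthcare seeking are not sparse (smallest expected counts 17.9 and 6.5), and all three printed values are larger than the uncorrected chi-square gives.

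**Conclusion.** The point holds as a gap in specification with one visible consequence. The SAP fixes neither a sparse-table rule nor the continuity correction, although 12 of 19 outcome tables are sparse by the usual criterion. No Table 2 conclusion changes under Fisher's test. Infant antiviral use is fragile: it rests on three events, and its p-value runs from 0.033 to 0.132 over the tests in Step 3. It should not stand as an unqualified significant difference.

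Separately, three Table 3 p-values are inconsistent with their own counts under the stated test. ARI remains significant and the other two remain non-significant, so no conclusion at 0.05 changes from correcting them. All of this assumes that the printed counts and denominators are correct. If they are not, the counts rather than the p-values need correcting.

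**What to change.** 1. Add to the Statistical analysis section: Fisher's exact test (two-sided) when any expected count is below 5, and the chi-square test without continuity correction otherwise.
2. Rerun Tables 2 and 3 under that rule. The 12 sparse rows take the Fisher values in Step 2.
3. Amend the text under Estimation of IVE in infants so that antiviral use is no longer listed as an unqualified significant difference. If it is discussed, give the counts (0 versus 3) and say that the result depends on the test.
4. Check the source data for the three inconsistent rows. If the counts are right, ARI becomes 0.0034 and healthcare seeking 0.071 (both chi-square). Hospitalization, which is sparse, becomes 0.407 (Fisher), equal to pneumonia.

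The cost is one sentence, a rerun of two tables and a small text change. Fisher's test is somewhat conservative, and one secondary result loses significance. Because the data are already known, the change should be labelled as made after the results were seen.

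### The SAP defines IVE but names no deciding primary analysis, and the document reports opposite verdicts on influenza in the same 636 women

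*SAP*

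**What the plan says.** The SAP's Statistical analysis section describes the primary twice. It first names an endpoint ("The primary outcome of the study was influenza" onset in pregnant women). It then gives the aim as to "estimate the average rate of influenza for each group (vaccinated versus unvaccinated" group), which is two rates.

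Four routes to a vaccine comparison are described, and none is ranked above the others:

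- a chi-square test between vaccinated and unvaccinated women;
- logistic regression with a random intercept, introduced by "We have used a Bayesian model selection for logistic" regression models;
- a beta-binomial model with one probability for each vaccination group;
- the IVE formula, one minus the ratio of the two incidence rates.

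The groups are explicitly compared ("We compared the vaccinated pregnant women" group with the unvaccinated group), and age is the other variable named ("The second variable was the age group"). For the selection step the section gives no candidate models, criterion, model prior or coefficient prior. Non-informative priors are mentioned only for the beta parameters. The one significance rule is a p-value "of 0.05 or less were considered statistically significant. IVE against influenza was" then defined by its formula.

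Under Estimation of IVE in pregnant women, the comparison of 6/406 with 6/230 is reported with the words "however the difference was not statistically significant. Similarly, higher rates of" other events. The same subsection concludes from the regression that "influenza vaccination added a statistically significant protection to pregnant women". The infant subsection makes the same claim, while Table 3 gives p = 0.59.

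**The concern.** When several analyses address one primary question, a plan has to say which of them decides and by what rule. This one does not. Its p-value rule fits the chi-square test but gives no reading for a posterior distribution. The IVE estimate has no stated interval method, and the regression comes from a selection procedure that cannot be reconstructed.

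At stake is the main conclusion. A reader can take from the document either that no difference was shown or that protection was significant, for the same outcome in the same women, and the SAP offers no basis for preferring one. The infant result has the same problem.

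**Working it through.** **Inputs.** Mothers (Table 2): 6/406 vaccinated, 6/230 unvaccinated. Infants (Table 3): 4/281 and 4/193. The document states no prior or selection criterion for the regression, so those used in step 5 are assumptions.

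**1. Figures that reproduce.** Pearson chi-square without continuity correction, mothers: 636 × (6×224 − 6×400)² / (406 × 230 × 12 × 624) = 1.014, p = 0.314, as printed. Infants: 474 × (4×189 − 4×277)² / (281 × 193 × 8 × 466) = 0.290, p = 0.590, as printed. The maternal IVE point estimate is 1 − 1.47/2.6 = 43.5% from the rounded rates, or 43.3% from the counts.

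**2. The IVE interval.** SE(log RR) = √(1/a − 1/n₁ + 1/b − 1/n₀).

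- Mothers: RR = (6/406)/(6/230) = 0.567 and SE = 0.571. IVE = 1 − 0.567 × exp(±1.96 × 0.571), which runs from −74% to 82%.
- Infants: RR = 0.687 and SE = 0.701, so IVE is 31% (−171% to 83%).

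The printed intervals (28.4% to 55.6%, and 4% to 51%) do not follow from these counts. The maternal one implies SE = ln(0.716/0.444)/3.92 = 0.12; the infant one implies ln(0.96/0.49)/3.92 = 0.17.

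**3. The regression contrast.**

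- Mothers: log OR = ln[(6×224)/(6×400)] = ln 0.56 = −0.58, SE 0.583, 95% CI −1.72 to 0.56.
- Infants: log OR = ln(189/277) = −0.38, 95% CI −1.78 to 1.02.

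The printed value is −4.2 in both groups. The vaccinated arm's own logit is ln(6/400) = −4.20 in mothers and ln(4/277) = −4.24 in infants. The printed figure therefore matches a level in one arm, not a difference between arms.

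**4. A two-group Bayesian version.** With independent Beta(1,1) priors (assumed), the maternal posterior has median IVE 43%, 95% interval −67% to 81%, and P(lower rate in the vaccinated) = 0.85. This agrees with the chi-square verdict.

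**5. What selection could do if vaccination were open to removal.** The likelihood-ratio statistic for vaccination is 0.975 in mothers and 0.286 in infants. BIC odds in favour of dropping it are exp[(ln N − LR)/2].

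| | Penalty on all subjects | Penalty on events |
|---|---|---|
| Mothers | 15.5 (N = 636) | 2.1 (N = 12) |
| Infants | 18.9 (N = 474) | 2.5 (N = 8) |

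With a normal prior on the maternal log OR and equal prior model odds, the probability that vaccination is included is 0.49, 0.43, 0.27, 0.16, 0.09 and 0.03 at prior SD 0.5, 1, 2.5, 5, 10 and 31.6.

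Exact enumeration at true rates 6/406 and 6/230 gives the repeat-sampling behaviour. The mean is taken on the log RR scale with 0.5 added to events and denominators.

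| Assumed criterion | Vaccination kept | Mean IVE when kept |
|---|---|---|
| BIC, N = 636 | 6% | 82% |
| BIC, events | 29% | 69% |

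Over all repeats the mean IVE is 43%.

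**The case against.** A reader might infer that no vaccine contrast is fixed at all, or that the data and the prior decide whether an effect is estimated. The document does not support either reading. The IVE formula is an explicit contrast, its population of 636 women is stated, and the chi-square test and the two-group beta-binomial model yield a comparison whatever the regression selects. Only the logistic model could lose the vaccination term. The SAP does not say that this term was open to removal, and both regressions report a vaccination result. Selection may have acted only on age or on the random intercept.

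Three further points stand:

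- The reported 43.5% is the crude formula and carries no selection bias.
- The false significance claim traces more directly to −4.2 being an arm-level logit; a correctly computed regression would have agreed with p = 0.314.
- Several routes add little false-positive risk by themselves. Under a common rate of 12/636, the chi-square, Wald risk-ratio and two beta-posterior contrasts each reject in 2.4% to 5.2% of samples, and at least one of them rejects in 5.4%.

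It can also be said that a criterion chosen now is chosen after the counts are known. That is true, but the proposed contrast is the one the SAP already defines, and every correctly computed route above gives the same answer.

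None of this supplies the missing designation, interval method or Bayesian criterion. Correcting −4.2 would remove the present conflict but leave no rule for a future one.

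**Conclusion.** The point holds as a specification defect with a visible consequence. A contrast exists, but nothing makes it decisive, and opposite verdicts on the primary endpoint stand side by side. From the printed counts alone, only the non-significant verdict is supported: IVE 43% (about −74% to 82%) in mothers and 31% (about −171% to 83%) in infants, by log-Wald intervals on unadjusted risk ratios.

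Removal of the vaccination term by selection is a possibility the SAP does not exclude, not something it states. The range of 6% to 29% kept, with mean IVE of 82% to 69% when kept, depends on the assumed BIC penalties and on true rates equal to those observed. It is not evidence that the reported estimates are inflated. The finding does not depend on it.

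**What to change.** Amend the Statistical analysis section as follows:

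- Name IVE = 1 − risk ratio, vaccinated versus unvaccinated in the 636 women, as the single primary contrast.
- Estimate it from one fixed model with vaccination forced in and no selection on it. List any covariates in full; age group is the only one the outcome model now names.
- State the interval method, and use one criterion: a two-sided 95% interval for IVE that excludes 0. The method must be stated, because the printed intervals exclude 0 while intervals derived from the counts do not.
- Apply the same model to the 474 infants as a secondary analysis.
- Label the other analyses of the same outcome, including the beta-binomial model, as sensitivity analyses.

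In the Results, withdraw both significance claims drawn from the regression and report one verdict for each population.

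The cost is SAP wording and one run of a simpler model on existing data. The downside is a less favourable reported result.

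### Vaccination is a fixed 0/1 with no minimum interval to illness or delivery and no rule for in-season vaccination, so exposure can be misclassified in both IVEs

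*SAP*

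**What the plan says.** In the Statistical analysis section, the vaccination variable records whether a woman has "been vaccinated (value =1) or not (value =0". Women are followed for the "entire influenza season, regardless of onset of influenza or ILI. The analysis was" then confined to that season. Each woman stays in one group throughout.

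The pre-season reasons for exclusion include "loss to follow-up, post-partum influenza vaccination (cocooning), pregnancy" discontinuation and perinatal loss. The only one that concerns vaccination timing is post-partum vaccination. None concerns a short interval between injection and season onset, illness or birth.

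IVE is one minus the "incidence rate of influenza in vaccinated women" divided by the same quantity in unvaccinated women. The Results compare influenza "between vaccinated women (6/406; 1.47%) and unvaccinated women (6/230; 2.6"%).

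For infants (Results, Estimation of IVE in infants), the exposed group is the 281 whose mothers were vaccinated while pregnant, against 193 whose mothers were not. Any birth before or during the season qualifies.

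**The concern.** A fixed indicator treats a woman as vaccinated for the whole season, whenever the injection was given. Three kinds of error can follow.

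- Influenza that begins before the injection, or too soon after it for protection, counts as a vaccinated case. This lowers IVE.
- An infant born a day after the mother's injection counts as exposed, like one born months later. If such infants are not yet protected, IVE is diluted.
- For a woman vaccinated during the season, the earlier influenza-free weeks count as vaccinated. This raises IVE.

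These errors work in opposite directions, so the net effect cannot be assumed. With 6 cases in vaccinated women and 4 in exposed infants, the placement of one case changes either reported figure substantially.

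**Working it through.** **Inputs.** Women: 6/406 vaccinated, 6/230 unvaccinated (Table 2). Infants: 4/281 exposed, 4/193 unexposed (Table 3). Formula: IVE = 1 − (risk in vaccinated ÷ risk in unvaccinated).

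**Step 1: reproduce the reported figures.**
- Women: 1 − (6/406)/(6/230) = 43.3%. The rounded rates give 1 − 1.47/2.6 = 43.5%, as reported.
- Infants: 1 − (4/281)/(4/193) = 31.3%, against 31.4% reported.

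Both are crude proportions by ever/never status, with no person-time.

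**Step 2: check whether a lag was applied without being stated.**
- 406 + 230 = 636 women and 281 + 193 = 474 infants, so nobody in either set was left out for a short interval.
- 6 + 6 = 12 and 4 + 4 = 8, so every positive test reported was counted.
- The 230 are all described as having refused vaccination, so no late-vaccinated woman was moved to that group.
- The 94 earlier exclusions are fully itemised (65 + 25 + 3 + 1), and none is for a short interval.

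**Step 3: check whether short intervals are plausible.** Table 1 reads "Mean gestational age, weeks (range) 19.3 (3-39) 21.6 (3-39) 0.003". These women had not delivered when the season began. Gestational age at birth in the infant set reached 42 weeks: "range: 28-42 weeks). There were 281 (59.3%) infants whose mothers were" vaccinated. Two assumptions are needed: that Table 1 gives age at enrollment, and that vaccination was at or after enrollment. A vaccinated woman enrolled at 39 weeks then had at most about 42 − 39 = 3 weeks to delivery. Her injection was at most about 3 weeks before season onset, or during the season.

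The first assumption is well supported. The Results give the same 3–39 week range for all 855 women and label it as age at enrollment. The means also fit: (855 × 23.3 − 406 × 19.3 − 230 × 21.6) ÷ 219 = 7117.7 ÷ 219 = 32.5 weeks for the women outside the 636, as expected if they enrolled late in pregnancy and delivered before the season. The second assumption is not stated in the document.

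**Step 4: sensitivity to one early case (scenarios, not counts).**
- Women, case dropped: 1 − (5/406)/(6/230) = 52.8%.
- Women, woman reclassified as unvaccinated: 1 − (5/405)/(7/231) = 59.3%.
- Infants, case dropped with denominator unchanged: 1 − (3/281)/(4/193) = 48.5%.

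**Step 5: the opposite direction.** Suppose an assumed 5% or 10% of the vaccinated group is excluded and contains no case.
- Women: 1 − (6/386)/(6/230) = 40.4%; 1 − (6/365)/(6/230) = 37.0%.
- Infants: 1 − (4/267)/(4/193) = 27.7%; 1 − (4/253)/(4/193) = 23.7%.

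**The case against.** The strongest reply is that the 0/1 coding only labels a model variable, and that the protocol, which is not shown, may define who counts as vaccinated. That would matter if the analysis had used such a definition. Step 2 shows that every woman, infant and reported case was counted by ever/never status, so the counts leave no room for one.

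A reader might infer that misclassification has been demonstrated. It has not. No vaccination, season or illness-onset dates are given. The 39-week argument rests on two assumptions, and the document's reference to a history of vaccination in 2019-2020 leaves room for vaccination before enrollment. The maximum of a range establishes only one woman, and nothing shows that any of the 6 or 4 cases was early. Nor can the number of late-enrolled mothers be estimated from their mean of 28.3 weeks, because no SD is reported.

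A reader might also say that exposure has no time window at all. That goes too far: analysis is confined to the season, pre-season post-partum vaccination is excluded, and infant exposure must fall within pregnancy. What is missing is a minimum lag and a rule for status that changes during the season.

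Two further points stand. Wald intervals on the log risk ratio run from −73.6% to 81.5% (women) and −171.3% to 82.6% (infants), so these shifts are small beside sampling error. And with the results known, replacing the primary exposure definition would be a post hoc change. Both limit the remedy, but neither justifies leaving the rule unstated.

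**Conclusion.** The concern holds as a weakness in the exposure rule that the SAP states and the analysis applied. Both IVEs can be affected. The number misclassified and the direction of bias cannot be determined from the document.

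The single-case scenarios show how much depends on the rule: 43.3% becomes 52.8% or 59.3% in women, and 31.3% becomes about 48.5% in infants. If the excluded group held no case, both estimates would fall instead. That short intervals occurred rests on Table 1 giving age at enrollment, which the document supports, and on vaccination at or after enrollment, which it does not state.

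**What to change.** Using the recorded vaccination, illness-onset and delivery dates:

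- Report IVE in women with vaccination as time-varying: time before the injection is unvaccinated, a stated lag after it is excluded, and later time is vaccinated. The lag could be 14 days. That figure is an assumption, not taken from the document, and should be labelled so.
- For infants, count as exposed only those born at least the stated lag after maternal vaccination, and say how the others are handled.
- Because results are known, present this beside the any-time classification and label it post hoc.
- Report how many women, infants and influenza cases fall inside the lag, and how many women were vaccinated after season onset. If all these counts are zero, the sponsor can say so and the point closes.

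The cost is SAP wording and a re-run, provided the dates were recorded. Precision falls slightly, because some time, women or infants leave the comparison.
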